## 4.2 Exclusion Criteria

- Subjects with active CNS metastases are excluded. If CNS metastases are treated and subjects are at neurologic baseline for at least 2 weeks prior to enrollment, they will be eligible but will need a Brain MRI prior to enrollment. Subjects must be off corticosteroids or on a dose of less than 10mg per day.
- Subjects with active, known or suspected autoimmune disease. Subjects with vitiligo, type I diabetes mellitus, residual hypothyroidism due to autoimmune thyroiditis only requiring hormone replacement, or conditions not expected to recur in the absence of an external trigger are permitted to enroll.
- Subjects with a condition requiring systemic treatment with either corticosteroids (>10 mg daily prednisone equivalent) or other immunosuppressive medications within 14 days of enrollment. Inhaled or topical steroids, and adrenal replacement steroid doses > 10 mg daily prednisone equivalent, are permitted in the absence of active autoimmune disease.
- Prior therapy with anti-PD-1, anti-PD-L1, anti-PD-L2, anti-CD137, or anti-CTLA-4 antibody (including ipilimumab or any other antibody or drug specifically targeting T-cell costimulation or checkpoint pathways).
- Prior therapy with ibrutinib or other BTK inhibitors.
- Previous or concurrent cancer within 3 years prior to treatment start EXCEPT for curatively treated cervical cancer in situ, non-melanoma skin cancer, superficial bladder tumors [Ta (non-invasive tumor), Tis (carcinoma in situ) and T1 (tumor invades lamina propria)].
- Known history of human immunodeficiency virus (HIV) infection or acquired immunodeficiency syndrome (AIDS).
- Serologic status reflecting active hepatitis B or C infection. Patients who are hepatitis B core antibody positive and who are antigen negative, will need to have a negative PCR result prior to enrollment. Those who are hepatitis B antigen positive or PCR positive, will be excluded.
- Subjects with Child Pugh B or C cirrhosis.
- History of severe hypersensitivity reactions to other monoclonal antibodies
- Substance abuse, medical, psychological or social conditions that may interfere with the patient's participation in the study or evaluation of the study results.
- History or concurrent condition of interstitial lung disease of any grade or severely impaired pulmonary function.
- Unresolved toxicity higher than CTCAE grade 1 attributed to any prior therapy or procedure, excluding alopecia.
- Clinically significant cardiovascular disease such as uncontrolled or symptomatic arrhythmia, congestive heart failure, any Class 3 or 4 cardiac disease as defined by the New York Heart Association Functional Classification, or history of myocardial infarction within 6 months prior to first dose with study drug

- Unable to swallow capsules or disease significantly affecting gastrointestinal function and/or inhibiting small intestine absorption such as; malabsorption syndrome, resection of the small bowel, or poorly controlled inflammatory bowel disease affecting the small intestine.
- Requires anticoagulation with warfarin or equivalent vitamin K antagonists (e.g. phenprocoumon).
- Requires treatment with a strong CYP3A4/5 and/or CYP2D6 inhibitor.
- History of stroke or intracranial hemorrhage within 6 months prior to enrollment.
- Any illness or medical conditions that are unstable or could jeopardize the safety of the patient and his/her compliance in the study.
- Major surgery or a wound that has not fully healed within 4 weeks of enrollment.
- Vaccinated with live, attenuated vaccines within 4 weeks of enrollment
- Has a history of (non-infectious) pneumonitis that required steroids or current pneumonitis within 6 months

#### **Excluded Therapies and Medications for Cancer**

- Anticancer chemotherapy during the study or within 4 weeks of study enrollment. Subjects must have recovered from the toxic effects of the previous anti-cancer chemotherapy (with the exception of alopecia). Anti-cancer therapy is defined as any agent or combination of agents with clinically proven anti-tumor activity administered by any route with the purpose of affecting the malignancy, either directly or indirectly, including palliative and therapeutic endpoints.
- Hormonal therapy during the study or within 2 weeks of first study enrollment.
- Radiotherapy to target lesions during study or within 2 weeks of enrollment.
- An irradiated lesion is considered evaluable only if it has shown enlargement since the completion of last radiation.
- Bone marrow transplant or stem cell rescue.
- Investigational drug therapy outside of this trial during or within 4 weeks of first study treatment.

#### **4.3 Withdrawal of Subjects from Study**

Subjects **must be withdrawn from the trial** (treatment and procedures) for the following reasons:

- Subject withdraws consent from study treatment and study procedures. A subject must be removed from the trial at his/her own request or at the request of his/her legally acceptable representative. At any time during the trial and without giving reasons, a

subject may decline to participate further. The subject will not suffer any disadvantage as a result.

- Pregnancy. Pregnancies will be reported to Janssen and Merck within 24 hours of having knowledge of the event. Pregnancy will not be reported as an SAE but the subject must be withdrawn from the trial immediately. (Note: subjects who have been withdrawn from treatment with study drug because of pregnancy should not undergo CT scans [with contrast]/MRI or bone scans while pregnant.)
- If, in the investigator's opinion, continuation of the trial would be harmful to the subject's well-being.
- Subject is lost to follow-up.
- Death.

All subjects who discontinue should comply with protocol specified follow-up and survival procedures. The ONLY exception to this requirement is when a subject withdraws consent for all study procedures or loses the ability to consent freely (i.e., is imprisoned or involuntarily incarcerated for the treatment of either a psychiatric or physical illness). If a subject was withdrawn before completing the study, the reason for withdrawal must be entered on the appropriate case report form page.

Subjects **may be** withdrawn from study treatment for the following reasons:

- The subject is non-compliant with ibrutinib administration as measured by a dosing diary, pembrolizumab administration, or trial procedures; including the use of anti-cancer therapy not prescribed by the study protocol.
- Severe allergic reaction to ibrutinib or pembrolizumab.
- The development of a second cancer.
- Development of an illness or situation which would, in the judgment of the investigator, significantly affect assessments of clinical status and trial endpoints.
- Deterioration of ECOG performance status to 3 or 4.
- Use of illicit drugs or other substances that may, in the opinion of the investigator, have a reasonable chance of contributing to toxicity or otherwise skewing trial result.

Any subject removed from the trial will remain under medical supervision until discharge or transfer is medically acceptable.

Any subject with progression of disease will come off of treatment except for patients deriving clinical benefit as deemed by the principal investigator with a maximum of 24 months on therapy. In all cases, the reason for withdrawal must be recorded in the CRF and in the subject's medical records.

#### **4.3.1 Screen Failures/Dropouts/Replacements**

A subject who discontinues study participation prematurely for any reasons except death, disease progression and severe toxicity is defined as a dropout. A subject who, for any reason (e.g., failure to satisfy the selection criteria), terminates the study before the time point used for the definition of “dropout” (see above) is regarded a “screening failure”. Subjects who withdraw from treatment (for any reason) during dose seeking phase may be replaced. Patients will be

considered inevaluable for the primary endpoint of disease control rate if they do not have at least one post-baseline disease response assessment. Inevaluable patients may be replaced.

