## 6.5 End of Treatment Visit and Follow up

### *End of Treatment Visit*

The end of treatment visit should be conducted when it is confirmed by the investigator that the patient will receive no further doses of drug on study.

- History and assessment to include brief examination, vital signs (heart rate, respiration rate, temperature and BP) and review of systems
- Toxicity/AE assessment
- ECOG Performance Status Assessment
- Hematology (hemoglobin, HCT, RBC, WBC with differential (neutrophils, bands, lymphocytes, monocytes, eosinophils and basophils) and platelet count
- Chemistry (ALT, AST, AP, total bilirubin, direct bilirubin, LDH, creatine kinase, lipase, amylase glucose, calcium, phosphate, magnesium, bicarbonate, sodium
- Radiologic assessment: CT scan or MRI (chest, abdomen, pelvis) with tumor measurement and disease assessment of non-measurable disease according to RECIST 1.1 and irRC criteria (please see Appendix B) may be conducted if it has not been performed within the last 4 weeks.

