- h. Hepatitis B surface antigen, surface antibody, and Hepatitis C antibody
- i. Pregnancy test will be performed at baseline for WOCBP and then only as clinically indicated
- j. After off treatment following disease progression survival f/u, can be performed over the phone every 3 months
- k. Archival tissues ( 10 unstained slides) if available
- l. The PBMC should be viably frozen (for flow cytometric analysis) and the plasma frozen separately .The actual analyses used will be based on response and determined by the investigator at a later date. Two green top (Sodium Heparin) tubes (about 20 ml) will be used each time. This will ONLY be collected at the screening and at the beginning of the 3rd cycle.
- m. If a subject discontinues treatment due to confirmed PD, only the EOT disease assessment is required if it has been > 4 weeks since the last disease assessment
- n. The safety follow-up visit will be approximately 30 days after the last dose or prior to the start of a subsequent anti-cancer therapy.

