### 9.3 Analysis Sets

All subjects who receive at least one dose of the study medication will be included in the safety evaluation.

All subjects who undergo at least one staging reassessment will be used for efficacy evaluations.

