### **Tumor response**

Tumor response data will be summarized for dosed subjects with measurable disease at baseline.

Objective response rate, disease control rate and PFS will be summarized in the expansion phase arm.

Tumor response will be analyzed using RECIST 1.1 criteria (Appendix B) and the immune response criteria. Confirmation of immune response will be done at the discretion of the investigator.

In this classification, the overall response is determined as follows:

- Immune response CR (irCR) is a complete disappearance of all lesions (whether measurable or not, and no new lesions) with confirmation by a repeat, consecutive assessment no less than 4 weeks from the first documentation.
- Immune response PR (irPR) is a decrease in tumor burden of greater than or equal to 50% relative to baseline. This must be confirmed by a consecutive assessment at least 4 weeks after the first documentation.
- Immune response SD (irSD) is classified as those who do not meet criteria for irCR or irPR and who do not have irPD
- Immune response PD (irPD) is an increase in tumor burden of greater than or equal to 25% relative to the minimum recorded tumor burden which must be confirmed by a repeat, consecutive assessment no less than 4 weeks from the first documentation.

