### **Definitions**

**Evaluable for toxicity.** All patients will be evaluable for toxicity from the time of their first treatment with ibrutinib or pembrolizumab.

**Evaluable for objective response.** Only those patients who have measurable disease present at baseline, have received at least one cycle of therapy, and have had their disease re-evaluated will be considered evaluable for response. These patients will have their response classified according to the definitions stated below. (Note: Patients who exhibit objective disease progression prior to the end of cycle 1 will also be considered evaluable.)

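### Treated patients with no post-baseline assessment drop out of the primary disease control rate and may be replaced, even after early death or decline, so the reported 4-month rate tends to be too high

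*Combined protocol and SAP*

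**What the plan says.** Section 4.3.1 states that patients are "considered inevaluable for the primary endpoint of disease control rate if they do not have at least one post-baseline disease response assessment", and then that "Inevaluable patients may be replaced". Section 9.3 sets the efficacy population in the same way: "All subjects who undergo at least one staging reassessment will be used for efficacy evaluations". Section 3 plans phase II in terms of 32 evaluable patients.

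Three other places bear on who is counted:

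- Section 4.3.1 mentions death, progression and toxicity only when it defines a term: "A subject who discontinues study participation prematurely for any reasons except death, disease progression and severe toxicity is defined as a dropout". The evaluability rule does not use that term.
- Appendix B (Definitions), on evaluability for objective response, adds that "Patients who exhibit objective disease progression prior to the end of cycle 1 will also be considered evaluable".
- Section 9.7 (Tumor response) uses another base: "Tumor response data will be summarized for dosed subjects with measurable disease at baseline". Its next sentence lists the disease control rate without saying whether that base applies.

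The first scheduled scan is at the start of cycle 3 in Section 6.4 and in the calendar column of Section 6.6. Calendar footnote c has both that timing and a scan after every three cycles. The end-of-treatment scan "may be conducted if it has not been performed within the last 4 weeks" according to Section 6.5. The calendar marks it as scheduled, and footnote m says of patients stopping for confirmed progression that "only the EOT disease assessment is required if it has been > 4 weeks since the last disease assessment".

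Section 9.2 gives the decision rule: at least 1 of 18 controlled at 4 months to continue and at least 4 of 32 to call the therapy effective, with rates of 5% and 20% and both error limits at 0.10.

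**The concern.** Whether a patient is counted depends on something that happens after treatment starts and is linked to the outcome. Patients who die or become too ill before any assessment are close to certain failures for disease control at 4 months. The plan removes them and lets another patient take the place.

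None of the apparent safeguards closes this gap. The exception for death, progression and toxicity governs only the word dropout. The Appendix B note needs objective progression before the end of cycle 1 and concerns objective response, so it does not reach a patient who dies or declines without a scan. Section 4.3 asks patients who discontinue to comply with follow-up, and end-of-treatment scans would shrink the group, but neither can produce an assessment in a patient who has died or is too ill.

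The trial has one arm, so there is no control group in which the same exclusion would operate. Few successes decide it, and the result will be read as the rate in treated patients. The error favors passing stage 1 and declaring the combination effective. Because the sections name different bases, the denominator could also be chosen after the data are seen.

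**Working it through.** **Inputs.** From Section 9.2: n1 = 18, continue if at least 1 controlled; N = 32, effective if at least 4 controlled; rates 5% and 20%; alpha and beta 0.10. From Section 5.1: 3-week cycles. Assumed, because the documents do not give them: d, the share of treated patients never assessed (5% to 20%), and c, the true 4-month control rate in those patients.

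**The plan's own design.** With X1 ~ Bin(18, p) and X2 ~ Bin(14, p), P(effective) = sum over x = 1 to 18 of P(X1 = x) × P(X2 ≥ 4 − x). This gives 0.0721 at p = 0.05 and 0.9015 at p = 0.20. P(stop at stage 1) = (1 − p)^18 = 0.397 at p = 0.05. A search confirms that 32 is the smallest maximum sample size meeting both limits. The stated design is correct.

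**Window for loss before assessment.** The start of cycle 3 is week 6. After three cycles is week 9.

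**Effect on the estimate.** If c = 0, the reported rate is the treated-patient rate multiplied by 1/(1 − d). This is the upper bound. Working back, a reported 4/32 = 12.5% corresponds to 12.5% × (1 − d) of treated patients, and the 32 assessed patients come from 32/(1 − d) treated.

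**Effect on the test, if 5% describes treated patients.** The rate among assessed patients is then p = (0.05 − d·c)/(1 − d). For example, d = 10% and c = 0 give 0.05/0.90 = 0.0556. Putting p into the two-stage formula:

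| d | 4/32 as share of treated | Treated per 32 assessed | Type I error, c = 0 | Type I error, c = 2.5% | P(stop at stage 1), c = 0 |
|---|---|---|---|---|---|
| 0 | 12.5% | 32 | 0.072 | 0.072 | 0.397 |
| 5% | 11.9% | 33.7 | 0.084 | 0.078 | 0.378 |
| 10% | 11.25% | 35.6 | 0.097 | 0.084 | 0.357 |
| 15% | 10.6% | 37.6 | 0.114 | 0.092 | 0.336 |
| 20% | 10.0% | 40 | 0.134 | 0.101 | 0.313 |

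Type I error reaches 0.10 at d = 10.9% when c = 0 and at d = 19.6% when c = 2.5%. With c = 5% (unassessed patients no different from the rest) it stays at 0.072 throughout.

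**If 5% and 20% describe evaluable patients.** Type I error is 0.072 whatever d is. Only the reading of the estimate as a treated-patient rate is overstated.

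**The case against.** The best defense is that the plan consistently means a response-evaluable population. Sections 3, 4.3.1 and 9.3 all point that way and the rule is fixed in advance, so the 5% and 20% can be read as rates in evaluable patients and the error rates hold. That reading is reasonable and stands as far as type I error goes. Section 9.2 does not state it, though, and it does not correct the estimate for treated patients.

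The second point is size. The synopsis expects 10% attrition. Even if all of that were unassessed failures, type I error would be 0.097, still under 0.10, and 4/32 would mean 11.25% rather than 12.5%. Entry requires ECOG 0 or 1 and an expected survival above 3 months, which also argues against the upper half of the assumed range. This is fair: the effect is modest at the plan's own attrition figure. But that figure is not tied to missing assessments, and a survival expectation above 3 months does not rule out death or decline before week 6 or 9.

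Third, many declining patients could still be assessed, because scans are allowed when clinically indicated and one is marked at end of treatment. This narrows the group but leaves in it those most certain to be failures. Footnote m adds little here, since patients with confirmed progression have normally already been assessed.

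Fourth, replacement is optional and is not the source of the bias. That is correct: the exclusion causes it, and replacement only restores the count to 32.

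**Conclusion.** The concern holds. As written, a treated patient who dies or declines before any assessment leaves the primary endpoint and can be replaced, and the reported 4-month rate then tends to overstate the rate in treated patients. The inflation is at most a factor of 1/(1 − d), which is 1.11 at d = 10% and 1.25 at d = 20%.

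Whether the planned 0.10 is breached depends on two things that the documents leave open. It happens only if the 5% null describes treated patients and more than 10.9% are unassessed failures, or 19.6% if those patients have half the null rate. The gap in the wording is certain; the size of the effect rests on assumed values of d and c. Patients who withdraw for reasons unrelated to disease would add little or no bias. This should be fixed, but it does not invalidate the design.

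**What to change.** - Apply the 1/18 and 4/32 rules to all eligible patients who receive at least one dose at the phase II dose, including the phase I patients carried over under Section 9.2.
- Count any patient without documented CR, PR or SD at 4 months as not controlled, and do not replace treated patients for the primary endpoint.
- Report the assessed-only rate as a sensitivity analysis, with the number of unassessed patients and the reasons.
- Align Sections 4.3.1, 9.3 and 9.7 to this denominator, and state in Section 9.2 that 5% and 20% refer to it.
- Reconcile Sections 6.4 and 6.5 with calendar footnotes c and m on scan timing and the end-of-treatment assessment. Name the scan and window that define 4 months (about week 17). Section 6.4 gives scans at weeks 6, 15 and 24; scanning after every three cycles gives weeks 9 and 18.

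**Cost.** Mainly wording. If 20% already describes treated patients, no patients are added: 32 treated, against 35.6 treated to obtain 32 assessed at d = 10%. If 20% was meant for assessed patients and the unassessed all fail, the treated rate is 0.20 × (1 − d), and power with 32 treated falls from 0.901 to 0.876, 0.846, 0.810 or 0.768 at d = 5%, 10%, 15% or 20%. Keeping 90% power would then need re-sizing: at d = 10%, the same search for 5% against 18% gives a maximum of 36. Counting withdrawals as failures is conservative, which the sensitivity analysis will show.

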#### **4.3.2 Removal of Patients from Protocol Therapy**

Patients will be removed from study when any of the criteria listed

- Disease progression
- Intercurrent illness that prevents further administration of treatment
- Unacceptable AE(s)
- Patient decides to withdraw from the study **OR**
- General or specific changes in the patient's condition render the patient unacceptable for further treatment in the judgment of the investigator

Notify the Principal Investigator and document the reason for study removal and the date the patient was removed in the eCRF. The patient should be followed per protocol

### **5. Treatment Plan**

#### **5.1 Drug Administration**

##### **Ibrutinib**

Ibrutinib should be administered orally once daily with a glass of water at approximately the same time each day. The capsules should be swallowed whole with water and should not be opened, broken, or chewed. Ibrutinib must not be taken with grapefruit juice or Seville orange juice

Ibrutinib drug product is a white opaque, size 0, hard gelatin capsule marked with "ibr 140 mg" in black ink, containing 140 mg of ibrutinib. Ibrutinib capsules are supplied in a white HDPE bottle with a child-resistant closure containing 90 or 120 hard capsules. Keep ibrutinib out of the sight and reach of children.

**Ibrutinib Capsules, 140 mg** should be stored according to the storage conditions indicated on the label. The recommended storage condition for ibrutinib capsules is 15°C to 25°C (59°F to 77°F) with excursions permitted to 30°C (86°F).

##### **Pembrolizumab**

Pembrolizumab is provided as a white to off white lyophilized powder (50 mg/vial) or as a liquid solution (100 mg/vial) in Type I glass vials intended for single use only.

Pembrolizumab Powder for Solution for Infusion, 50 mg/vial, is reconstituted with sterile water for injection prior to use. The drug product is stored as a stable lyophilized powder or liquid solution under refrigerated conditions (2 to 8°C).

The lyophilized drug product after reconstitution with sterile water for injection, and the liquid drug product are a clear to opalescent solutions, essentially free of visible particles. The reconstituted lyophilized product and the liquid product are intended for IV administration. The reconstituted drug product solution or the liquid drug product can be further diluted with normal saline or 5% dextrose in the concentration range of 1 to 10 mg/mL in intravenous (IV) containers made of polyvinyl chloride (PVC) or non-PVC material. Reconstituted vials should be immediately used to prepare the infusion solution in the IV bag and the infusion solution should be immediately administered. Diluted pembrolizumab solutions may be stored at room temperature for a cumulative time of up to 4 hours. This includes room temperature storage of admixture solutions in the IV bags and the duration of infusion. In addition, IV bags can be stored at 2 to 8°C for up to a cumulative time of 20 hours. This recommendation is based on up to 24 hours of room temperature and up to 24 hours of refrigerated stability data of diluted MK-3475 solutions in the IV bags.

